5.10 Protocol Deviations

AbbVie does not allow intentional/prospective deviations from the protocol except when necessary to eliminate an immediate hazard to study subjects. The investigator is responsible for complying with all protocol requirements, written instructions, and applicable laws regarding protocol deviations. Protocol deviations are prohibited except when necessary to eliminate an immediate hazard to study subjects. If a protocol deviation occurs (or is identified, including those that may be due to the COVID-19 pandemic), the investigator is responsible for notifying IEC/IRB, regulatory authorities (as applicable) and AbbVie. In Japan, the investigator will record all protocol deviations in the appropriate medical records at the site.

6 SAFETY CONSIDERATIONS

6.1 Complaints and Adverse Events

Complaints

A complaint is any written, electronic, or oral communication that alleges deficiencies related to the physical characteristics, identity, quality, purity, potency, durability, reliability, safety, effectiveness, or performance of a product/device. Complaints associated with any component of this investigational product must be reported to AbbVie.

Product Complaint

A product complaint is any complaint related to the drug component of the product.

For a product this may include, but is not limited to, damaged/broken product or packaging, product appearance whose color/markings do not match the labeling, labeling discrepancies/inadequacies in the labeling/instructions (e.g., printing illegible), missing components/product, or packaging issues.

Product complaints concerning the investigational product must be reported to AbbVie within 1 business day of the study site's knowledge of the event. Product complaints occurring during the study will be followed up to a satisfactory conclusion.

Reporting will be done via electronic data capture (EDC). The date the product complaint details are entered into EDC and the form is saved represents the date reported to AbbVie. A back-up paper form will be provided for reporting complaints related to unassigned product or in the event of an EDC system issue. If a back-up paper form is used, the date the form is emailed to [contact] represents the date reported to AbbVie.

All follow-up information is to be reported to the sponsor (or an authorized representative) and documented in source as required by the sponsor. Product complaints associated with adverse events will be reported in the study summary. All other complaints will be monitored on an ongoing basis. Product complaints occurring during the study will be followed up to a satisfactory conclusion.

Medical Complaints/Adverse Events and Serious Adverse Events

An AE is defined as any untoward medical occurrence in a subject or clinical investigation subject administered a pharmaceutical product and which does not necessarily have a causal relationship with this treatment. An AE can therefore be any unfavorable and unintended sign (including an abnormal laboratory finding), symptom, or disease temporally associated with the use of a medicinal (investigational) product, whether or not the event is considered causally related to the use of the product.

The investigators will monitor each subject for clinical and laboratory evidence of AEs on a routine basis throughout the study. All AEs will be followed to a satisfactory conclusion.

An elective surgery/procedure scheduled to occur during a study will not be considered an AE if the surgery/procedure is being performed for a pre-existing condition and the surgery/procedure has been

pre planned prior to study entry. However, if the pre-existing condition deteriorates unexpectedly during the study (e.g., surgery performed earlier than planned), then the deterioration of the condition for which the elective surgery/procedure is being done will be considered an AE.

If an adverse event, whether associated with study drug or not, meets any of the following criteria, it is to be reported to AbbVie clinical pharmacovigilance as a serious adverse event within 24 hours of the site being made aware of the serious adverse event (refer to Section 4.3 of the Operations Manual for reporting details and contact information):

Death of Subject An event that results in the death of a subject.

Life-Threatening An event that, in the opinion of the investigator, would have

resulted in immediate fatality if medical intervention had not been taken. This does not include an event that would have been fatal if it

had occurred in a more severe form.

Hospitalization or Prolongation of Hospitalization An event that results in an admission to the hospital for any length of time or prolongs the subject's hospital stay. This does not include an emergency room visit or admission to an outpatient facility.

Congenital Anomaly An anomaly detected at or after birth, or any anomaly that results in

fetal loss.

Persistent or Significant Disability/Incapacity

An event that results in a condition that substantially interferes with the activities of daily living of a study subject. Disability is not intended to include experiences of relatively minor medical significance such as headache, nausea, vomiting, diarrhea, influenza, and accidental trauma (e.g., sprained ankle).

Important Medical Event
Requiring Medical or Surgical
Intervention to Prevent
Serious Outcome

An important medical event that may not be immediately lifethreatening or result in death or hospitalization, but based on medical judgment may jeopardize the subject and may require medical or surgical intervention to prevent any of the outcomes listed above (i.e., death of subject, life threatening, hospitalization, prolongation of hospitalization, congenital anomaly, or persistent or significant disability/incapacity). Additionally, any elective or spontaneous abortion or stillbirth is considered an important medical event. Examples of such events include allergic bronchospasm requiring intensive treatment in an emergency room or at home, blood dyscrasias or convulsions that do not result in inpatient hospitalization, or the development of drug dependency or drug abuse.

All AEs reported from the time of study drug administration until 30 days after discontinuation of study drug administration will be collected, whether solicited or spontaneously reported by the subject. In addition, SAEs and protocol-related nonserious AEs will be collected from the time the subject signs the study-specific informed consent.

The following definitions will be used for Serious Adverse Reactions (SAR) and Suspected Unexpected Serious Adverse Reaction (SUSAR):

SAR Defined as all noxious and unintended responses to an IMP related to any dose

administered that result in an SAE as defined above.

SUSAR Refers to individual SAE case reports from clinical trials where a causal

relationship between the SAE and the IMP was suspected by either the sponsor or the investigator, is unexpected (not listed in the applicable Reference Safety

Information) and meets one of the above serious criteria.

AbbVie will be responsible for Suspected Unexpected Serious Adverse Reactions (SUSAR) reporting for the Investigational Medicinal Product (IMP) in accordance with global and local guidelines.

Adverse events will be monitored throughout the study to identify any of special interest that may indicate a trend or risk to subjects.

Adverse Events of Special Interest

The following AEs of special interest will be monitored during the study:

- Serious infections
- Opportunistic infections
- Herpes Zoster
- Active TB
- Malignancy (all types)
- Adjudicated Gastrointestinal Perforations
- Adjudicated MACE
- Anemia
- Neutropenia
- Lymphopenia
- Renal dysfunction
- Hepatic disorder
- Elevated CPK
- Adjudicated Embolic and thrombotic events (non-cardiac, non-central nervous system [CNS])

In addition to the AESIs listed above, the following adverse events will also be monitored during the study: Bone Fracture; Retinal detachment.

Adverse Event Severity and Relationship to Study Drug

Investigators will rate the severity of each AE according to the National Cancer Institute Common Terminology Criteria for Adverse Events (CTCAE) version 5.0, which can be accessed at: http://ctep.cancer.gov/protocolDevelopment/electronic applications/ctc.htm#ctc.

If no grading criteria are provided for the reported event, then the event should be graded follows:

Mild (Grade 1) Asymptomatic or mild symptoms; clinical or diagnostic observations only;

intervention not indicated

Moderate (Grade 2) Minimal, local or noninvasive intervention indicated; limiting age-

appropriate instrumental activities of daily living (ADL)

Severe (Grade 3 – 5)

Grade 3 Severe or medically significant but not immediately life-threatening;

hospitalization or prolongation of hospitalization indicated; disabling; limiting self-care ADL (self-care ADL refer to bathing, dressing and undressing, feeding self, using the toilet, taking medications, and not

bedridden)

Grade 4 Life-threatening consequences; urgent intervention indicated

Grade 5 Death related to AE

The investigator will assess the relationship of the AE to the study drugs upadacitinib (or matching placebo) and prednisone/prednisolone (or matching placebo). Summary of CS-related AEs will be based on this assessment.

The investigator will use the following definitions to assess the relationship of the AE to the use of study drug:

Reasonable Possibility – After consideration of factors including timing of the event, biologic plausibility, clinical judgment, and potential alternative causes, there is sufficient evidence (information) to suggest a causal relationship.

No Reasonable Possibility – After consideration of factors including timing of the event, biologic plausibility, clinical judgment, and potential alternative causes, there is insufficient evidence (information) to suggest a causal relationship.

For causality assessments, events assessed as having a reasonable possibility of being related to the study drug will be considered "associated." Events assessed as having no reasonable possibility of being related to study drug will be considered "not associated." In addition, when the investigator has not reported a causality or deemed it not assessable, AbbVie will consider the event associated.

If an investigator's opinion of no reasonable possibility of being related to study drug is given, another cause of event must be provided by the investigator for the SAE.

Pregnancy

While not an AE, pregnancy in a study subject must be reported to AbbVie within 1 working day of the site becoming aware of the pregnancy. If a pregnancy occurs in a study subject information regarding the pregnancy and the outcome will be collected.

Subjects should avoid pregnancy throughout the course of the study, starting with the Screening Visit through 30 days after the last study drug administration for female subjects. Results of a positive pregnancy test or confirmation of a pregnancy will be assessed starting with the Screening Visit through the final study visit.

Subjects who become pregnant during the study must be discontinued (Section 5.5).

The pregnancy outcome of an elective or spontaneous abortion, stillbirth or congenital anomaly is considered a SAE and must be reported to AbbVie within 24 hours of the site becoming aware of the event.

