In ORAL Surveillance, a study of a different JAK inhibitor, tofacitinib, in RA patients 50 years of age and older with at least one cardiovascular risk factor, higher rates of all-cause mortality, malignancies, MACE and thrombosis (overall thrombosis, deep vein thrombosis, and pulmonary embolism) were seen in patients treated with tofacitinib versus TNF blockers. These higher rates were primarily observed in patients 65 years of age and older, patients with a history of atherosclerotic cardiovascular disease, and patients with other cardiovascular risk factors (such as current or past long-time smokers). Although upadacitinib clinical trial data to date have not indicated a higher risk for MACE, venous thromboembolism, malignancies excluding NMSC, or deaths in RA patients treated with upadacitinib versus adalimumab, the findings of the ORAL Surveillance study may potentially also apply to other JAK inhibitors and an increased risk for these events compared to TNF blockers cannot be completely excluded. Therefore, the investigator should consider the benefits and risks of upadacitinib treatment and suitable treatment alternatives in determining study participation and the continued use of upadacitinib in patients 65 years of age and older, patients with a history of atherosclerotic cardiovascular disease or other cardiovascular risk factors, patients who are current or past long-time smokers, and/or patients with other malignancy risk factors (e.g., current malignancy or history of malignancy).

The results of genetic toxicology testing indicate that upadacitinib is not genotoxic; however, upadacitinib is teratogenic based on animal studies, which necessitates avoidance of pregnancy in females of childbearing potential. Based on the calculated safety margins for human fetal exposure with seminal fluid transfer, there is judged to be no risk to the pregnancy of female partners of male subjects who are treated with upadacitinib.

A detailed discussion of the pre-clinical and clinical toxicology, metabolism, pharmacology, and safety experience with upadacitinib can be found in the current Investigator's Brochure. 18

Taken together, the safety and efficacy data from upadacitinib studies to date show a favorable benefit:risk profile for upadacitinib and support the continued investigation of upadacitinib in patients with various autoimmune/inflammatory conditions.

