5.6 Follow-Up for Study Drug Discontinuation or Subject Withdrawal from Study

Discontinuation of Study Drug and Continuation of Study Participation

Following discontinuation of study drug, the subject should be treated in accordance with the investigator's best clinical judgment, irrespective of whether or not the subject decides to continue participation in the study.

If a subject prematurely discontinues study drug, the procedures outlined for the Premature Discontinuation Visit (PD Visit) should be completed as soon as possible, preferably within 2 weeks, and preferably prior to initiation of another therapy. In addition, a 30-Day Follow-up Visit after the last dose of study drug is required to ensure all treatment-emergent AEs/serious adverse events (SAEs) have been

resolved. The Follow-Up Visit is not applicable for subjects who discontinued study drug and continued study participation and completed at least 1 study visit at least 30 days after last dose of study drug.

To minimize missing data for efficacy and safety assessments, subjects who prematurely discontinue study drug treatment should continue to be followed for all regularly scheduled visits for the period from which they discontinue as outlined in the Activity Schedule (Appendix D), unless subjects have decided to discontinue the study participation entirely (withdrawal of informed consent). That is, subjects who discontinue study drug during Period 1 should continue to follow the visit schedule for the remainder of Period 1, but not continue into Period 2. Subjects who discontinue study drug during Period 2, should follow the visit schedule for the remainder of Period 2. As noted in the Activity Schedule (Appendix D), at the visits after study drug discontinuation, subjects should adhere to all study procedures except for dispensing study drug or reviewing returns and accountability, dispensing/reviewing study drug instructions, dosing diaries, pharmacokinetic sample collection, and sample collection for exploratory research. Subjects should be advised on the continued scientific importance of their data even if they discontinue treatment with study drug early.

Premature Discontinuation of Study (Withdrawal of Informed Consent)

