10.2.1 Treatment-Emergent Adverse Events

Unless noted otherwise, all summaries included treatment-emergent AEs (TEAEs) only. TEAEs are defined as any event that begins or worsens in severity after initiation of study drug through 30 days post-study drug dosing. Events where the onset date is the same as the study treatment start date are assumed to be treatment-emergent. All treatment-emergent AEs will be summarized overall, as well as by primary MedDRA SOC and Preferred Term. The SOCs will be presented in alphabetical order, and the PTs will be presented in alphabetical order within each SOC.

The number and percentage of subjects experiencing treatment-emergent AEs will be summarized.

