10.3 Analysis of Laboratory Data

Selected clinical laboratory tests defined in the protocol operations manual (e.g., hematology, clinical chemistry) will be summarized on SS1 for Period 1 and SS LT for long term.

Baseline is defined as the last non-missing measurements recorded on or before the date of the first dose of study drug. For the analysis of laboratory data, values observed within 30 days of the last dose of study drug will be included.

Each laboratory variable will be summarized for all time points (starting with Baseline) with the number of non-missing observations, mean and standard deviation, median, minimum and maximum. Mean change from Baseline to each applicable post-baseline visit will be summarized for selected laboratory variables, with the number of observations, Baseline mean, and visit mean. In Period 1, mean change from Baseline will be compared between treatment groups using a one-way Analysis of Variance (ANOVA), with treatment as a fixed factor. The change from Baseline mean, standard error, and 95% confidence interval will be presented for the mean change from Baseline within each treatment group and difference between treatment groups.

[figure not shown]
Laboratory abnormalities will be evaluated based on Potentially Clinically Important (PCI) criteria (Appendix C). For each laboratory PCI criterion, the number and percentage

of subjects who have a laboratory value meeting the criteria will be summarized. Listings will be provided to summarize subject-level laboratory data for subjects meeting PCI criteria.

Changes in laboratory parameters will be tabulated using shift tables by National Cancer Institute (NCI) Common Terminology Criteria (CTC) (version 4.03). Selected lipid parameters will be summarized using National Cholesterol Education Program (NCEP) Adult Treatment Panel III (ATPIII) guidelines (Appendix D). A shift table from Baseline to the worse value during treatment will be created. A similar shift table will be provided to summarize shifts from Baseline to the final post-baseline value.

In addition, ALT/SGPT, AST/SGOT, alkaline phosphatase, and total bilirubin will be categorized as follows:

- ALT $> 3 \times ULN$
- ALT $> 5 \times ULN$
- $ALT > 10 \times ULN$
- $ALT > 20 \times ULN$
- $AST > 3 \times ULN$
- $AST > 5 \times ULN$
- AST $> 10 \times ULN$
- $AST > 20 \times ULN$
- $TBL > 2 \times ULN$
- Alkaline phosphatase (ALP) $> 1.5 \times ULN$
- ALT and/or AST $> 3 \times ULN$ and TBL $> 1.5 \times ULN$

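### For subjects who stop study drug but keep attending visits, the end of safety collection is unclear, and events of special interest starting after day 30 are left out of the by-arm comparisons

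*Protocol*

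**What the plan says.** **Follow-up.** Protocol 5.6 gives the reason for continued visits: "To minimize missing data for efficacy and safety assessments, subjects who prematurely discontinue study drug treatment should continue to be followed". Subjects remain on the schedule of the period in which they stopped. The procedures waived off drug (Protocol 5.6 and Appendix D, Note 2) concern drug dispensing and accountability, instructions, diaries, PK and exploratory samples. AE assessment and safety laboratory tests are not waived, and Appendix D schedules AE assessment at every visit.

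**Collection.** Protocol 6.1 limits general collection: "All AEs reported from the time of study drug administration until 30 days after discontinuation of study drug administration will be collected". It then adds that "SAEs and protocol-related nonserious AEs will be collected from the time the subject signs the study-specific informed consent", which gives a start and no end. The same section says "The investigators will monitor each subject for clinical and laboratory evidence of AEs on a routine basis throughout the study". It requires SAE reporting for any AE that, "whether associated with study drug or not, meets any of the following criteria, it is to be reported to AbbVie clinical pharmacovigilance", and states no post-dose limit there.

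**Analysis.** SAP 10.2.1 restricts AE summaries, unless otherwise noted, to treatment-emergent events, meaning any event that "begins or worsens in severity after initiation of study drug through 30 days post-study drug dosing". SAP 10.3 applies the same limit to laboratory data ("values observed within 30 days of the last dose of study drug will be included"), and SAP 10.4 does so for vital signs. There are two exceptions. SAP 10.2.2 counts deaths more than 30 days after the last dose, and SAP 10.2.5 lists all SAEs separately from treatment-emergent ones.

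**The concern.** The off-drug visits have a stated safety purpose, but the collection rule and the analysis window both close about a month after dosing. Protocol 2.2 reports that a study of another JAK inhibitor found "higher rates of all-cause mortality, malignancies, MACE and thrombosis" than with TNF blockers. It notes that upadacitinib data in rheumatoid arthritis have not shown this against adalimumab, but that the risk cannot be excluded. It also says that non-melanoma skin cancer has been observed at increased risk with upadacitinib. Some of these events can begin or come to light well after dosing stops.

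Stopping drug is a post-randomisation event whose frequency and reasons may differ between arms. A by-arm comparison cut off shortly after stopping may therefore differ from one over all randomised follow-up. With rare events, one or two omitted cases can change how the comparison looks. The collection text also leaves sites to choose between a 30-day limit and monitoring for the whole study, and they may choose differently.

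**Working it through.** The plan gives no figure to reproduce here, so the check is a comparison of texts followed by an illustration of size.

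**Step 1: follow a late event through the rules.** Take a subject who stops drug in Period 1, stays on study, and has an event with onset after day 30.

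| Event | Collected under Protocol 6.1? | In SAP outputs? |
|---|---|---|
| Death | Yes, as an SAE if SAE collection has no end | Counted (10.2.2) |
| Stroke, myocardial infarction or other serious event | Probably: reportable whatever its relation to drug, no end date stated | Listing of all SAEs (10.2.5); not in the 10.2.6 comparisons |
| Skin cancer or deep vein thrombosis treated as an outpatient and meeting no seriousness criterion | Outside the 30-day rule | Not in the 10.2.6 comparisons |

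The last row can occur because the hospitalisation criterion in Protocol 6.1 excludes emergency-room visits and outpatient admissions. An investigator could still judge such a case an important medical event. Protocol 6.1 monitors all types of malignancy, and SAP 10.2.6 gives non-melanoma skin cancer its own category.

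The last column follows from the default in SAP 10.2.1. SAP 10.2.6 states no exception for its tables, event rates, forest plot or Kaplan-Meier curves. It also plans listings of these events without saying whether they run past day 30. Under SAP 10.2.4, exposure time ends at last dose plus 30 days. The rates are therefore coherent as on-treatment rates, but they do not describe the whole of follow-up.

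**Step 2: scheduled follow-up beyond the window.** The uncovered time is the period end minus (stop week + 30/7), with visits from Appendix D.

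| Stop week | Window ends (week) | Uncovered weeks | Visits beyond |
|---|---|---|---|
| 4 | 8.3 | 43.7 | 8 |
| 12 | 16.3 | 35.7 | 6 |
| 24 | 28.3 | 23.7 | 3 |
| 36 | 40.3 | 11.7 | 2 |
| 44 | 48.3 | 3.7 | 1 |
| 56 (Period 2) | 60.3 | 43.7 | 4 |
| 80 (Period 2) | 84.3 | 19.7 | 2 |

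**Step 3: patient-time, illustration only.** Assume that a fraction d of the planned 420 subjects stop, that stop times are uniform over 52 weeks, and that all who stop stay to Week 52.

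- Mean uncovered time per subject who stops = (52 − 30/7)² / (2 × 52) = 47.71² / 104 = 21.9 weeks.
- Uncovered patient-years = 420 × d × 21.9/52, out of 420 (counting 52 weeks as one year).
- d = 10%: 42 × 21.9/52 ≈ 17.7 patient-years, 4.2%.
- d = 20%: 35.4, 8.4%.
- d = 30%: 53.0, 12.6%.
- d = 40%: 70.7, 16.8%.

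**Step 4: events.** At an assumed 0.5 to 2 events per 100 patient-years, the expected number of uncovered events of one type runs from 17.7 × 0.005 ≈ 0.1 to 70.7 × 0.02 ≈ 1.4.

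**The case against.** A reader might infer that late malignancy, MACE and thrombosis are lost, or that off-drug follow-up yields no analysed safety data apart from deaths. The documents do not support either. SAE collection has no stated end, and SAEs are reportable whether or not related to drug. AE assessment continues at every visit, and all SAEs are listed. MACE as defined (cardiovascular death, non-fatal infarction or stroke), and many malignancies and thromboses, would normally be serious. Nor does a diagnosis six weeks after the last dose by itself mean exclusion: the treatment-emergent definition turns on when an event begins or worsens, so one with recorded onset inside the window still counts.

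A reader might also infer that the comparison is biased in a known direction. That is not shown. Under Protocol 5.8, a flare in Period 1 does not by itself end study drug, since subjects on escape corticosteroid continue blinded treatment. This weakens any argument from flare to differential stopping.

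The 30-day analysis window is also a defensible choice. After stopping, subjects receive therapy chosen by the investigator, possibly tocilizumab, so later events are harder to attribute. Finally, Operations Manual Section 4.3 and the cardiovascular adjudication charter are not available here and may settle the SAE end date or the adjudication of late events.

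All of this stands. It does not remove the conflict within the protocol text or the gap for non-serious events. It also does not turn a listing into a comparison by arm. An end date in the Operations Manual would not change the SAP's analysis window.

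**Conclusion.** The point holds as an unresolved inconsistency in collection and a truncated by-arm analysis. Protocol 6.1 ends general AE collection at 30 days and leaves the SAE end open, while Protocol 5.6, other text in 6.1 and Appendix D imply safety assessment for as long as the subject attends. Late non-serious events of special interest lie outside the stated collection window. Any event of special interest starting after day 30 is by default missing from the SAP 10.2.6 comparisons.

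The range of 18 to 71 patient-years rests entirely on the assumed stopping fraction, uniform stop times and full retention, none of which the documents give. The expected number of omitted events of any one type is small, about 0.1 to 1.4 at the assumed rates. This warrants a clarification and a supplementary analysis. It does not undermine the planned treatment-emergent analysis.

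**What to change.** **Protocol 6.1.** Reconcile the 30-day rule with Protocol 5.6, the whole-study monitoring text in 6.1, and Appendix D. State that, for subjects off drug but on study, SAEs, deaths and the malignancy, MACE and embolic or thrombotic events of special interest are collected through the last visit of that period. State that they are adjudicated where adjudication applies.

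**SAP 10.2.6.** Keep the treatment-emergent analysis primary. Add a supplementary summary on SS1 of these events through Week 52, over time on study, by treatment group.

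**Cost.** Modest. The visits already exist, and so does the adjudication process. There is some extra reporting for off-drug subjects. The summary will also include events arising on later standard-of-care therapy, which is why it should remain supplementary. SAP 9.1 already counts 428 subjects enrolled, so some Period 1 follow-up may predate any protocol change. If so, the summary should say how completely late non-serious events were captured.
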